Fig. 4: Uptake and Retention of [³H]AraG and [³H]F-AraC in Resting and Activated Human Primary T Cells. Human primary T cells were isolated from PBMC buffy coats, activated in culture for 2 days, and incubated with either [³H]AraG or [³H]F-AraC to measure uptake (a) and retention (b); n=3 per treatment per tracer). Both tracers were taken up at significantly higher levels (~6-7 fold) in activated versus resting T cells (**p<0.001). In contrast, [³H]AraG was retained at significantly higher levels (~30% more) within both resting and activated T cells versus [³H]F-AraC (*p<0.05). Data in all graphs are expressed as mean ± SD.

A 2-day activation protocol of sorted (~94% CD3+ T cells; data not shown) human peripheral blood mononuclear cells (PBMCs) resulted in similar morphological changes as seen in murine T cells. Significantly higher uptake in activated versus resting cells was seen with both [³H]AraG and [³H]F-AraC, but retention in both cell states was significantly higher with [³H]AraG (p<0.05; Fig. 4). Finally, we found significantly higher uptake (~19-fold) of [¹⁸F]F-AraG in activated versus resting human T cells (p<0.001; Fig. 5c). Although [¹⁸F]F-AraG effluxes significantly out of activated but not resting cells (p<0.05), absolute levels in activated versus resting cells at all time points evaluated were significantly higher (p<0.01). Overall these results support the use of [¹⁸F]F-AraG in selective PET imaging of activated versus resting T cells.

We have also evaluated whether [¹⁸F]F-AraG accumulates in cells via dCK and/or dGK activity using established cell lines [40]. Loss of dCK in mutant CCRF-CEM T lymphoblast cells (dCK⁻), as confirmed with Western blot analysis, (significantly impaired [¹⁸F]F-AraG uptake (p<0.001; Fig. 5a). Overexpression of dCK in mutant cells (dCK⁺) showed a trend toward increased tracer uptake compared to dCK⁻ cells (p=0.17), whereas dGK overexpression (dGK⁺) in dCK⁻ cells restored tracer uptake to levels seen in wild-type cells. No effects on tracer retention were seen across any of these cell lines (Fig. 5b).

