9 MEASUREMENTS

9.1 Primary and Secondary Outcome measures

Primary outcomes will be the severity/score of aGVHD or the development of aGVHD in the highly suspected and high risk groups respectively. Diagnosis and staging of the disease are ultimately based on skin, liver and gut involvement and will be further supported by the secondary outcome of IHC analysis of the gastrointestinal tract. The latter mostly focuses on the detection of dead regions as determined by haematoxylin and eosin staining. For this study, an additional secondary outcome will be to further stain tissues for T cell markers to determine T cell infiltration (CD3, CD4 and CD8) and T cell activation markers (e.g. OX40) to determine T cell status since activated T cells underlie the development of aGVHD in the early stages.

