9.1.1 Primary Outcome Measurement Methods

Static images acquired will be used to determine the bio-distribution of the imaging agent in the GVHD groups. Past images as well as newly acquired data from healthy subjects will be used as comparisons. Regions of interest will be drawn on various organs such as the liver, cervical lymph nodes and gut and quantified using imaging software (e.g. Inveon Research Workplace or Amide). In addition any areas that show up differently in the GVHD groups, to the normal bio-distribution seen in healthy subjects will be identified and ROIs will also be drawn over these regions.

Bio-distribution data will be expressed as % injected dose/gram (%ID/g) and/or as standard uptake values (SUV) with respect to the organ being studied. In the high suspected aGVHD group, [¹⁸F]F-AraG PET results will be compared to any grades and scores of aGVHD severity attributed to subjects. In the case of the high-risk group, after the second scan, patients will be monitored for development of aGVHD and the clinical endpoint (whether or not the high risk patient develop aGVHD) will represent the primary outcome variable. In addition, IHC analysis of biopsies taken in either GVHD group will help in the interpretation of the primary results and thus potentially support interpretation of the PET data. The IHC analysis will involve determining the amount of cell death or T cell infiltration and activation.

Vital signs and blood laboratory data collected before and after the i.v. injection of [¹⁸F]F-AraG will allow evaluation of any unexpected side effects.

To measure plasma radioactivity, whole blood sample will be centrifuged. The radiolabeled tracer concentration in whole blood, pellet post centrifugation and plasma will be measured by a gamma well counter (1-min per sample). The counting rates measured by the well counter will be converted to the PET equivalent counts using a conversion factor from a weekly phantom cylinder study. The counts should be decay corrected back to the injection time.

Plasma parent tracer and metabolite concentrations will be determined using solid phase extraction combined with HPLC technology.

Clinical assessment of disease severity will be made by the aGVHD grade. Staging and grading of the disease will be performed by Clinicians at the Bone Marrow and Transplant Clinic using the Glucksberg grade and International bone marrow Transplant Registry Severity Index (IBMTR) at time of enrollment and imaging.

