9.2 Secondary Outcome

Healthy subjects group: Biodistribution information and kinetic behavior of the radiotracer.

The secondary outcome is the IHC confirmation of abnormal T cell status in those patients who have had a biopsy.

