10.6.2 Analysis Plan

Although the study will have low power due to the constrained sample size, in addition to descriptive statistics we will perform Spearman rank correlation between the SUV values and IHC measurements in biopsy locations.

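### Section 10.6.2 plans only simple SUV-IHC correlations, so a positive SUV-OX40 correlation could reflect T-cell density and would not by itself support activation selectivity

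*Combined protocol and SAP*

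**What the plan says.** Section 10.6.2 gives the whole tissue analysis. Alongside descriptive statistics, "we will perform Spearman rank correlation between the SUV values and IHC measurements in biopsy locations". No partial correlation, activated-to-total ratio, joint model or comparison between markers is named.

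Section 9.1 distinguishes two quantities in the same tissue. The extra staining is "to determine T cell infiltration (CD3, CD4 and CD8) and T cell activation markers (e.g. OX40) to determine T cell status". Section 9.1.1 describes the IHC reading only as "determining the amount of cell death or T cell infiltration and activation"; it does not say whether activation is a count, a density or a share of the T cells present. Section 9.2 adds: "The secondary outcome is the IHC confirmation of abnormal T cell status in those patients who have had a biopsy".

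The rationale for the tracer is activation. Section 2.2 reports roughly 19-fold higher uptake in activated than in resting human T cells in culture and concludes that the results support its use "in selective PET imaging of activated versus resting T cells". The protocol title also calls it a tracer for activated T cells.

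On numbers, Section 10.7 allows up to 25 GVHD patients, roughly half in each group, and says that power is insufficient for formal tests. Section 3.1 encourages biopsy in the highly suspected group but does not require it.

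**The concern.** In culture, activated and resting cells are separated by design. In a biopsy they are mixed, and a site with more T cells may well have more CD3-positive and more OX40-positive cells. If so, SUV and OX40 can be correlated only because both follow CD3.

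The distinction drawn in Section 9.1 is then lost in Section 10.6.2: the same positive SUV-OX40 correlation could come from an activation tracer or from a tracer of T-cell density. Section 10.7 already expects high agreement between uptake and IHC. At stake is what the trial can say about activation, which is the reason for preferring this tracer to less specific imaging.

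**Working it through.** The plan has no figure to reproduce: no alpha, effect size or number of biopsies is stated. The check asks how often the planned correlation would look positive for a tracer with no activation effect.

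**Inputs from the protocol.** Up to 25 GVHD patients, roughly half per group (10.7): 25 / 2 = 12.5, so n = 12. The 19-fold ratio (2.2).

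**Assumed inputs.** Two-sided 5% level; n = 8 as a lower case because biopsy is optional; OX40 scored as an amount; correlations r of 0.6, 0.7 and 0.8 of SUV and of OX40 with CD3.

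**Model 1 (density-only tracer).** C ~ N(0,1) is CD3 density. SUV = rC + √(1−r²)·e1 and OX40 = rC + √(1−r²)·e2, with e1 and e2 independent. SUV and OX40 are then correlated at r² (0.36, 0.49, 0.64) through C alone.

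The expected sample Spearman for bivariate normal data is 6/[π(n+1)] × [asin ρ + (n−2)·asin(ρ/2)]. For n = 12 and ρ = 0.36: 0.1469 × (0.368 + 10 × 0.181) = 0.32. The other two cases give 0.44 and 0.58. The significance threshold at n = 12 is 2.228/√(10 + 2.228²) = 0.576.

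Share of simulated trials significant, two-sided:

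| | r = 0.6 | r = 0.7 | r = 0.8 |
|---|---|---|---|
| n = 12, simple SUV-OX40 | 19% | 33% | 57% |
| n = 8, simple SUV-OX40 | 14% | 22% | 37% |
| n = 12, partial Spearman given CD3 | 6% | 6% | 7% |
| n = 12, partial, CD3 error SD 0.5 (assumed) | 7% | 9% | 14% |

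The partial Spearman is (r_SO − r_SC·r_OC)/√[(1 − r_SC²)(1 − r_OC²)] on ranks, tested on n − 3 degrees of freedom.

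**Model 2 (different assumptions).** Log-normal density, an activated fraction with median 20%, and measurement noise in SUV and IHC; significant positive results counted, nominal 2.5%. At n = 12:
- Density-only tracer: SUV-OX40 amount significant in 19% to 87%, partial given CD3 in 7% to 15%.
- Tracer with the 19-fold ratio: SUV-OX40 amount significant in 84% to 95%, partial in 41% to 69%.
- When density drives most of the variation, the median simple correlation is 0.78 for the density-only tracer and 0.84 for the selective one, so the planned statistic barely separates them.

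**Precision of the partial correlation.** With a true partial correlation of 0.5 in Model 1, power is 20% to 22% at n = 8 and 33% to 35% at n = 12. For an observed 0.5 at n = 12, an approximate 95% interval is tanh(0.549 ± 1.96 × √(1.06/8)) = tanh(0.549 ± 0.713), or −0.16 to 0.85.

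**OX40-to-CD3 ratio.** In Model 1, read as log amounts, the log ratio is OX40 − C. For the density-only tracer its mean Spearman with SUV at n = 12 is about −0.23, because C enters with a negative sign. With a true partial correlation of 0.5, it is significant in only 5% to 6% of trials. The ratio and the partial correlation are not interchangeable.

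**The case against.** The strongest reply is that the trial does not set out to test selectivity. The Section 2.2 statement is preclinical background. Section 1.1 asks about uptake in GVHD regions. The secondary outcome in Section 9.2, abnormal T-cell status, covers infiltration as well as activation, and Section 9.1.1 gives IHC a supporting role. A tracer that followed infiltrating T cells would still serve the primary objective. This stands, and it limits the point to how one secondary correlation may be interpreted.

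The scoring of OX40 is also open. If it is scored as a share of CD3-positive cells, the density-only tracer in Model 2 gives a median correlation of about 0 and a significant positive result in about 2.5% of trials, so the problem disappears. That stands too, but the plan does not choose this scoring.

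The plan disclaims formal inference and sets no alpha, so the significance rates here measure how misleading the correlation could be; they are not error rates of a planned test. Low power, however, does not change what a simple correlation measures.

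A reader might infer that the plan correlates SUV with each marker separately and that a density tracer would therefore appear to confirm activation. The text says only IHC measurements. Pairwise use is the natural reading of Spearman, but the false confirmation is a possibility that depends on scoring and on how OX40 and CD3 vary together.

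**Conclusion.** The gap is real and modest. Section 9.1 plans stains for both infiltration and activation, and Section 10.6.2 has no analysis that separates them. A positive SUV-OX40 correlation could arise from density alone, in about 19% to 57% of trials at n = 12, if OX40 is scored as an amount and the correlations with CD3 are 0.6 to 0.8. Both conditions are assumptions; the documents neither state nor exclude them.

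The documents do not support the stronger inference that the trial claims to test activated-versus-resting selectivity in patients and must fail at it. What follows is narrower: the simple correlation would not by itself support activation selectivity and should not be reported as if it did.

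**What to change.** In Section 10.6.2:
- State which activation marker is used and how it is scored.
- Add an exploratory partial Spearman correlation of SUV with OX40 given CD3 at the same site, one site per patient, with a confidence interval.
- Report the simple SUV-CD3 correlation separately, as the infiltration result.
- State that a simple SUV-OX40 correlation does not show activation selectivity.
- Do not substitute the OX40-to-CD3 ratio as an equivalent.

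The cost is a few sentences. The stains are already planned, and the partial correlation needs no co-staining, although a per-cell share might. The limits are low precision in a small biopsied set and incomplete adjustment when CD3 is measured with error, so the result should be presented as an estimate with its interval. It is best settled before the scans and biopsies are read.

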These preliminary studies in healthy human volunteers have been promising with low background in the thorax and GI tract, making it favorable for thoracic and pelvic imaging. Favorable kinetics of [¹⁸F]F-AraG in humans along with the preclinical data support its potential as a promising tracer for early detection of GVHD and warrants its further clinical evaluation in aGVHD patients. Given the paucity of PET tracers for activated T cells in the clinic this work lays the important foundation for [¹⁸F]F-AraG PET imaging in aGVHD patients and the potential to provide crucial information to aid in the detection of activated T cell dynamics during the activation phase of aGVHD.

Organs	Male	Female
Adrenals	0.046567	0.067133
Brain	0.006380	0.007407
Breasts	0.005757	0.007547
Gallbladder Wall	0.051400	0.063033
LLI Wall	0.085107	0.012150
Small Intestine	0.047033	0.073000
Stomach Wall	0.018667	0.025367
ULI Wall	0.022600	0.033067
Heart Wall	0.052533	0.096933
Kidneys	0.877000	1.133333
Liver	0.211000	0.266667
Lungs	0.027167	0.033133
Muscle	0.009190	0.012167
Ovaries		0.016967
Pancreas	0.037300	0.050200
Red Marrow	0.013600	0.016833
Osteogenic Cells	0.007390	0.010593
Skin	0.004543	0.005790
Spleen	0.093600	0.163667
Testes	0.002780	
Thymus	0.005710	0.007800
Thyroid	0.001357	0.001633
Urinary Bladder Wall	0.085800	0.088167
Uterus	0.014133	0.017500
Total Body	0.018767	0.025200
Effective Dose	0.0138 mSv/MBq	

Table 2: [¹⁸F]F-AraG human radiation dosimetry data. Mean radiation dosimetry data in 3 males and 3 females in REM/mCi. The kidneys receive the highest radiation dose followed by the liver.

For our studies at Stanford, the tracer will be administered as a single bolus injection of approximately 5 mCi into a hand or arm vein. The rationale for the starting dose is based on dosimetry studies already performed in healthy human volunteers where the dose limiting organ was found to be the kidney and the annual dose characterized as 5mCi. Please refer to the imaging protocol for recommended limits for male and female subjects. The major route of clearance based on initial clinical studies is the liver and kidney.

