2.6 Study Design

Study participants will consist of healthy volunteers for extended studies on radiotracer behavior and patients belonging to a GVHD group. Two patient categories exist within the GVHD group-those highly suspected to have acute GVHD and those that are at high risk for developing acute GVHD. We will recruit healthy volunteers through local advertising. We will recruit high risk and confirmed GvHD patients from the Bone Marrow and Transplantation Clinic at the Stanford Cancer Institute.

Normal subjects will be recruited by publicly disseminating the information about the clinical trial through printed media such as a flyer, or by sending out an email to the Stanford community. We will ask for volunteers. A consent form for healthy volunteers is also included. Patients will undergo preliminary evaluation to ensure eligibility, receive and sign an informed consent, be enrolled in the trial, and then have [¹⁸F]F-AraG PET/CT.

Highly suspected acute GVHD patients will be scanned following biopsy (taken to confirm acute GVHD). The staging and grading of the disease using the Glucksberg grade and International bone marrow Transplant Registry Severity Index (IBMTR) at time of enrollment will be noted. Their consent for a PET-CT scan will be obtained prior to biopsy. Biopsy tissues of consented patients will be analyzed further for T cell involvement.

High-risk patients (recipients of myeloablative or reduced intensity allogeneic transplants using either bone marrow or peripheral blood stem cells from HLA-matched or HLA-mismatched related or unrelated donors-protocols 9917, 9142, 9022, 9924) will have to sign consent forms

before they undergo a transplant. All those that consent will undergo a PET-CT scan day 4 \pm 2 days post transplant. Additionally these patients will be scanned again between day 14-21 post transplant. Follow up on these patients will note those that go on to develop aGVHD and the clinical end point will be correlated to the scans to verify any predictive potential of the radiotracer.

For both GVHD groups-results of the scan will be compared to biopsy results and immunohistochemical staining of the biopsy samples for T cells.

Investigational agent: $[^{18}\text{F}]\text{F-AraG}$ will be formulated in a sterile and pyrogen-free isotonic solution will be administered in a single slow IV injection.

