4 IMAGING AGENT/DEVICE/PROCEDURE INFORMATION

4.1 $[18\text{F}]\text{F-AraG}$: 2'-deoxy-2'-[18F]fluoro-9- β -D-arabinofuranosyl guanine

The imaging agent to be used in this study is 2'-deoxy-2'-[18F]fluoro-9- β -D-arabinofuranosyl guanine. The radionuclide on this imaging agent being Fluorine-18 (^{18}F). The imaging agent will be administered intravenously.

Clinical grade imaging agent will be synthesized under GMP/GLP conditions at the Lucas Center Cyclotron and Radiochemistry facility, part of the Molecular Imaging Program at Stanford. The imaging agent will be requested as and when subjects become available. The radiotracer will be received at the Nuclear Medicine department at Stanford Hospital in a lead shielded container by an authorized person and with the appropriate transfer sheet.

Dosimetry of this imaging agent has previously been characterized in male and female healthy subjects and the information is included on page 21. Dosimetric calculations were performed

using the OLINDA/EXM 1.1 software using methods previously described using other tracers [Yaghoubi, 2001].

PET/CT is a well established, FDA approved clinical imaging procedure. Each subject will be scanned a maximum of 2 times. For each imaging session the amount of radioactivity that will be administered will be less than 5.7 and 4.4 mCi for males and females respectively.

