5 STUDY PROCEDURES

5.1 Imaging Protocol for Patient Groups

Each subject may have up to two imaging sessions. The procedures for each imaging session is detailed below:

Day 1 (Imaging Day)

Overview of procedures prior and post injection of [¹⁸F] F-AraG:

1. Subject will participate in an informed consent session (approximately 30 minutes) and if she/he would like to continue after being fully informed she/he will sign consent form.
2. Subject will be asked to drink several glasses of water before arriving at the nuclear medicine clinic and during the study.
3. Subject will be interviewed to obtain medical history.
4. Volunteer height and weight will be measured.
5. Baseline Heart Rate (HR), Blood Pressure (BP), Blood Oxygen %, Temperature, and Respiratory Rate will be collected at baseline (5-120 minutes prior to the injection of the tracer).
6. IV line may be placed in both arms of healthy subjects for PET tracer injection and another may be used for blood collection. The GVHD patients will have double lumen catheters which can these be used for these purposes.
7. For baseline CBC analysis- 3 ml of blood will be collected and 5 ml of blood will be collected for baseline metabolic panel analysis.
8. Subject may either be positioned on the PET/CT scanner bed or another bed in the clinic (where possible the same PET-CT system should be used especially for the healthy subjects).
9. Injection of [¹⁸F] F-AraG and post-injection procedures will follow.
10. If possible, subjects should be asked to urinate prior to the start of the PET/CT scans.
11. A bolus < 5.7 mCi of clinical grade [¹⁸F] F-AraG for male volunteers or < 4.4 mCi of clinical grade [¹⁸F]F-AraG for female volunteers will be injected through IV.
12. A CT image will be acquired with the PET images.
13. The PET scanning procedure may start at the time of tracer injection or at a later time point after tracer injection. The imaging field includes the vertex to thigh for healthy subjects and vertex to feet for GVHD patients. Up to two whole-body PET scans may be performed at various time points after injection of the tracer, not to exceed 2 hours after tracer injection.
14. Blood pressure, Temperature, Blood Oxygen saturation, Heart Rate, Respiratory Rate will be measured immediately after [¹⁸F]F-AraG PET-CT procedure.
15. A safety follow up will happen at one time point within the time interval (day 2 – day 7) post-scan.
16. All observed adverse events and subject complaints will be recorded.

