6 STUDY CALENDAR

6.1 Healthy Volunteers

Table 6-1: Study Calendar for Healthy Volunteers

	Screening	Day 1			Safety Follow-Up
	Day -30 to Day 1 pre-injection	Pre-injection of [¹⁸ F]F-AraG (Baseline)	Injection of [¹⁸ F]F-AraG ^a	Post-injection of [¹⁸ F]F-AraG	Day 2-7 post-scan
Inclusion/Exclusion Criteria	X				
Informed Consent	X ^d	X ^d			
hCG ^c	X ^d	X ^d			
Height		X			
Weight		X			
Vital signs		X		X	X
EKG		X (leads placed prior to scan)	X	X	
CBC w/diff, plts		X			X
Serum chemistry ^b		X			X
IV administration of [¹⁸ F]F-AraG			X		
PET/CT scan with investigational Agent [¹⁸F]F-AraG				X ^e	
Arterial/venous blood sampling for input function				X (0, 1, 3, 5 10, 15, 30, 45, 60 and 90 min after tracer injection)	
Radio-Metabolite Analysis				X (0, 1, 3, 5 10, 15, 30, 45, 60 and 90 min after tracer injection)	
Adverse event evaluation				X	X ^f

a: Investigational Agent: Dose as assigned (5 mCi); route/schedule.

b: Albumin, alkaline phosphatase, total bilirubin, bicarbonate, BUN, calcium, chloride, creatinine, glucose, LDH, phosphorus, potassium, total protein, SGOT[21], SGPT[45], sodium.

c: Urine or serum pregnancy test (women of childbearing potential).

d: Procedure may be done during screening period or on Day 1 prior to injection of study drug.

e: Scan 1: 30-minute dynamic PET of heart (60x5s+25x1min); Scan 2: vertex to mid-thigh static PET 60-minute post injection (includes brain); Scan 3: vertex to thigh static PET 90 minutes post-injection

f: Collected at one time point within the time interval (day 2 – day 7) post scan.

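### The nominal 5 mCi dose, given without regard to sex, is 14% above the protocol's own limit for women, and its description as an annual figure needs clarifying before Arm 2 opens

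*Combined protocol and SAP*

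**What the plan says.** **Nominal dose.** Section 2.2 states that "the tracer will be administered as a single bolus injection of approximately 5 mCi into a hand or arm vein". Its rationale is that "the dose limiting organ was found to be the kidney and the annual dose characterized as 5mCi". The next sentence reads "Please refer to the imaging protocol for recommended limits for male and female subjects". Footnote a of Table 6-1 reads "Investigational Agent: Dose as assigned (5 mCi); route/schedule", and Tables 6-2 and 6-3 carry the same footnote. None of these entries separates men from women.

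**Operative limits.** Section 4.1 says that the activity for each session "will be less than 5.7 and 4.4 mCi for males and females respectively". Step 11 of section 5.1 repeats both limits. Section 7.1 bases its radiation figures on 211 MBq for men and 163 MBq for women.

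**Number of injections.** Section 5.1 says "Each subject may have up to two imaging sessions". For the high-risk group (Arm 2), scanned first around day 4 after transplant, section 2.6 adds "Additionally these patients will be scanned again between day 14-21 post transplant". Step 15 of the GVHD patient protocol places this repeat 10 to 17 days after the first scan.

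**Dosimetry.** Table 2 gives kidney coefficients of 0.877 rem/mCi (male) and 1.1333 rem/mCi (female), and an effective dose of "0.0138 mSv/MBq" with no split by sex. Section 7.1 prints tracer doses of 2.7 mSv (female) and 3.3 mSv (male) per session.

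**The concern.** One protocol gives two incompatible activities for women. The calendars are working documents, and their footnotes carry no pointer to the sex-specific limits. The group-specific injection steps (healthy subject step 12, GVHD patient step 6) state no activity at all. Someone working from those steps and the calendar would find only 5 mCi. The excess falls on the kidney, which section 2.2 names as the dose-limiting organ, and section 7.1 says the exposure is for research only.

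The sentence that justifies the dose is also hard to reconcile with the schedule. If 5 mCi is what a participant may receive in a year, the male limit for a single session already allows more than that, and every Arm 2 patient who completes both scans would go well past it.

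**Working it through.** **Inputs.** Limits below 5.7 mCi (M) and below 4.4 mCi (F), from sections 4.1 and 5.1. Nominal 5 mCi, from section 2.2 and footnote a. Kidney coefficients 0.877 (M) and 1.1333 (F) rem/mCi and effective dose 0.0138 mSv/MBq, from Table 2. Activities of 211 and 163 MBq and doses of 3.3 and 2.7 mSv, from section 7.1. Conversion 1 mCi = 37 MBq.

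**1. Reproducing the protocol's limits.** Take limit = L / kidney coefficient with L = 5 rem. The 5 rem is an assumption; the documents do not print it.
- Male: 5 / 0.877 = 5.70 mCi
- Female: 5 / 1.1333 = 4.41 mCi

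Both limits are recovered. Section 7.1 uses the same activities: 211 / 37 = 5.70 mCi and 163 / 37 = 4.41 mCi. The limits, the kidney coefficients and section 7.1 therefore agree with one another.

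**2. Nominal dose against the limits.**
- Female: 5 / 4.4 = 1.136, so 14% above the limit. In activity, 5 × 37 = 185 MBq against 163 MBq.
- Female kidney: 5 × 1.1333 = 5.67 rem, against 4.4 × 1.1333 = 4.99 rem at the limit.
- Male kidney: 5 × 0.877 = 4.39 rem, against 5.7 × 0.877 = 5.00 rem at the limit. The nominal dose is acceptable for men.

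**3. The annual figure read as a yearly ceiling.**
- One male session may reach almost 5.7 mCi, which is above 5.
- Two Arm 2 injections at the nominal dose: 2 × 5 = 10 mCi.
- Two at the limits: below 2 × 5.7 = 11.4 mCi (M) and below 2 × 4.4 = 8.8 mCi (F).
- Kidney dose over two sessions at the limits, tracer only: 11.4 × 0.877 = 10.0 rem (M); 8.8 × 1.1333 = 9.97 rem (F).

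Read as a yearly ceiling, 5 mCi does not fit. Read as 5 rem to the kidney per injection, it fits both limits (step 1).

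**4. Effective doses in section 7.1.**
- Female: 163 × 0.0138 = 2.25 mSv; printed 2.7, ratio 1.20, implied coefficient 2.7 / 163 = 0.0166 mSv/MBq.
- Male: 211 × 0.0138 = 2.91 mSv; printed 3.3, ratio 1.13, implied coefficient 3.3 / 211 = 0.0156 mSv/MBq.

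The printed doses do not follow from Table 2, and section 7.1 names no coefficient.

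**The case against.** The strongest reply is that dosing is already controlled where it counts. Sections 4.1, 5.1 (step 11) and 7.1 all use the same sex-specific values. Section 2.2 says approximately and directs the reader to those limits, and the footnote refers to an assigned dose. Section 7.1 also has a researcher and a technologist double-check every dose. This stands, and it is why the point is minor: an overdose would require staff to bypass two sections and a check. It does not remove the conflict, because approximately 5 would have to stretch downward by more than (5 − 4.4) / 5 = 12% to be correct for any woman.

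A second reply is that 5 mCi is an average over the sexes. The midpoint of the limits is (5.7 + 4.4) / 2 = 5.05 mCi. With the mean kidney coefficient of 1.005 rem/mCi, the assumed 5 rem gives 4.97 mCi. That may explain where the figure came from, but an average is still not a permissible dose for women.

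A reader might infer that Arm 2 breaches an annual radiation limit, so that either the rationale or the schedule must be wrong. The documents do not support that. Section 2.2 describes the 5 mCi as a finding from healthy-volunteer dosimetry, does not call it a limit and does not apply it to Arm 2. No rem limit is printed, per session or per year. Section 7.1 also reports four earlier patients who received two doses each, with only mild side effects observed. What is shown is that the wording needs correcting.

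On effective dose, the coefficient behind section 7.1 may come from a dosimetry report outside these documents. The printed doses are higher than Table 2 implies, so Table 2 gives no sign that exposure is understated. Section 7.1 labels its figures as for one session, so the lack of a two-session total is not an error.

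**Conclusion.** The point holds at minor severity.

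- **Female dose (high confidence).** Section 2.2 and three calendar footnotes give 5 mCi to both sexes. For women that is 14% above the protocol's own limit, or 5.67 against 4.99 rem to the kidney. This rests only on printed figures.
- **Annual figure (moderate confidence).** As a yearly ceiling, 5 mCi is incompatible with the male limit and with Arm 2's two injections. A slip for 5 rem per injection would explain both limits, but that is an inference, and only the sponsor can settle it.
- **Effective dose (reconciliation only).** The printed 2.7 and 3.3 mSv are 20% and 13% above the products from Table 2. The documents do not show which is right.

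A reader might infer that women in the trial will be overdosed. The documents show an inconsistent instruction, with the correct limits stated elsewhere and a dose check in place; they do not show that anyone would receive too much. No endpoint or analysis changes.

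**What to change.** 1. In section 2.2 and in footnote a of Tables 6-1, 6-2 and 6-3, replace the single 5 mCi with a target and a cap for each sex. For example: men, approximately 5 mCi and always below 5.7 mCi; women, a sponsor-set target below 4.4 mCi. Printing the caps alone would remove the only stated target activity.
2. Before Arm 2 opens, ask the sponsor what the annual 5 mCi means. If it is a per-injection basis or a unit slip, reword the sentence accordingly and show how the limits follow from the Table 2 kidney coefficients. Amend the Arm 2 schedule or activity only if a true annual cap exists.
3. In section 7.1, state the mSv/MBq coefficient used and reconcile it with Table 2. Do not lower the printed doses until the source is confirmed.

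The cost is one sponsor query, one female target to be set, and wording changes in section 2.2, three footnotes and section 7.1. There are no new procedures unless an annual cap proves real. Section 10.8 plans to image and assess up to 10 Arm 1 patients before recruiting Arm 2, which leaves time for the query. The female-dose correction should not wait for that, because footnote a also governs healthy volunteers and Arm 1.
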